1. PURPOSE OF THE STUDY

a. Brief Summary

The purpose of the research study is to test a new approach for treating patients with snoring and obstructive sleep apnea (OSA). A special device (NAS-nasal stent) appears to be a useful alternative or additive treatment for patients with OSA.

b. Objectives

We hope to learn through this study if this device provides a better alternative treatment for obsturctive sleep apnea and snoring.

c. Rationale for Research in Humans

2. STUDY PROCEDURES

a. Procedures

This research study is seeking to enroll up to 30 participants with OSA and snoring. The enrollment will be at Stanford Sleep Medicine Center. The NAS (straight type) supports the soft palate from "collapsing" by supporting it physically, as well as securing the passage of airflow both inside and outside of the tube. Participants in the proposed study will undergo any or all of the following procedures.

After the consent process (30 min), each participant will be asked to complete either paper questionnaires which inquires about his or her demographic information and medical history (Sleep Disorders Questionnaire, 30 min) and level of daytime sleepiness in various situations (Epworth Sleepiness Scale, 5 min) or an electronic questionnaire (Alliance Sleep Questionnaire, 20 min).

Each participant will be asked to submit to an initial evaluation (60 min), which consists of a discussion of the participant's sleep habits and problems, medical history of participant and family, review of systems, medications, education, employment, and personal habits. A general physical examination, including but not limited to examination of the mouth and throat, and measurements of his or her weight and height; circumference of neck, waist, and hip; pulse and respiration rate; and blood pressure.

The participants will undergo two sleep studies: one sleep study at our center prior to using the NAS device (Baseline) and another after 7 days of use of the device at their

homes (Treatment). The participants will wear the NAS device during the second sleep study.

The sleep study will be conducted in routine fashion, with recording electrodes and equipment attached to the participant to enable monitoring of the electroencephalogram (EEG, C3-A2 and C4- A1, O2-A1 and O1-A2), electro-oculogram (EOG, ROC-A1, LOC-A2), chin and anterior tibialis electromyograms (EMG), heart rate by two-lead electrocardiogram (EKG), snoring intensity (anterior neck microphone), nasal pressure (nasal cannula), oral airflow(thermocouple), thoracic and abdominal movement (inductance plethysmography bands), and oxygen saturation (pulse oximetry). The duration of the application of all of these electrodes and recording devices to the participant is approximately 1.5 hours. The polysomnogram will be scheduled to allow at least 7 hours but no more than 9 hours of time in bed for the participant during the night.

The participants will be provided the following instructions for handling the NAS device: -Before handling the NAS, wash hands and nails thoroughly with soap. Make sure to thoroughly rinse off the soap as well. -Check NAS package carefully for breakage on the package. In case of breakage, do not use and contact the clinical research staff. -Check right or left nostril for intended insertion -Open NAS package, and take out NAS device. -Insert the tube to the appropriate side and slide NAS device slowly into the nasal airway. -Clip the stopper on to the nasal septum / bridge to secure the device. -Open the mouth in front of a mirror; check that there is the tip of the NAS device showing 3mm from the soft palate. -Go to sleep with the NAS applied. -Remove the NAS through nose and dispose once awake. -Limit use of this device to a maximum of 10 hours. Always dispose after use, and do not re-use. Use within six months.

Participants will have the option to to receive the nasal device after the second sleep study. The patient will be allowed to receive complimentary nasal stents until the time the device becomes commercially available. During this time, each participant will be asked to complete and submit the Epworth Sleepiness Scale every three months.

-Close out visit

After completion of the first sleep study (baseline) and second sleep study (treatment), subject will be asked to come back for a follow-up visit to discuss the results of his/her sleep studies with the study doctor, [name]. During this visit, the study doctor or research coordinator will ask the subject to place the nasal stent into his/her nostril, and the PI or research coordinator will then take pictures of the back of the subject's mouth, where the nasal stent should be resting. Subject's face will not be included in the photos. If after meeting with the study doctor and the subject would like to try the nasal stent in a different size, the subject may have a repeat treatment PSG.

b. Procedure Risks

The above procedures are in clinical use at our center. We are taking all necessary precautions for any risk that may occur in this clinical study.

c. Use of Deception in the Study

Not Applicable

d. Use of Audio and Video Recordings

Participants will be videotaped during the sleep study as per our usual sleep clinic protocol. The videotapes will be kept for 7 years and then destroyed.

e. Alternative Procedures or Courses of Treatment

Alternative treatments for obstructive sleep apnea will be discussed with the participant, including continuous positive airway pressure (CPAP), upper airway surgery, and oral appliance therapy. There are risks/benefits to all these alternative treatments that will be discussed with the participants; these are standard of care treatments.

f. Will it be possible to continue the more (most) appropriate therapy for the participant(s) after the conclusion of the study?

Yes

g. Study Endpoint(s)

The study will end after 30 participants are completed.

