A Disposable Device NAS to Treat Obstructive Sleep Apnea and Snoring

NCT02928770

December 5, 2014

[name], PhD, Principal Investigator Stanford University Stanford, California 94305

Statistical Analysis Plan

The primary endpoint that will be evaluated in the study would be the AHI efficacy of the NAS device by PSG comparisons. The PSG factors concerned will be compared between the two PSG evaluations conducted, the initial control PSG evaluation without the NAS device applied and the PSG evaluation with the NAS device applied.

As for the questionnaires, each questionnaire such as the ESS, the BQ, the MQ, the SSS, the SAQLI and etc., obtained will be analyzed for determining qualitative factors regarding quality of life and sleep qualities. In addition, these questionnaires and interviews will be valuable resources regarding safety issues as well.

The secondary endpoint that will be evaluated in the study would be the safety of the NAS device. Interviews and questionnaires would be the mode of evaluation regarding the safety factors. The ultimate goal of safety would be finishing this clinical study without any adverse events or accidents that harm the subjects physically.

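### No masked scoring of the sleep studies is planned, so scorer expectation could create or enlarge the AHI difference that is the primary endpoint

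*Protocol*

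**What the plan says.** The SAP defines the endpoint in one sentence: "The primary endpoint that will be evaluated in the study would be the AHI efficacy of the NAS device by PSG comparisons". The two sides of the comparison are "the initial control PSG evaluation without the NAS device applied and the PSG evaluation with the NAS device applied". There is no sham or parallel arm.

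Protocol section 2.a fixes the order: baseline first, then a second study after 7 days of home use. On device status it says "The participants will wear the NAS device during the second sleep study". Section 8.m places the second study at day 8. The sentence on conduct begins "The sleep study will be conducted in routine fashion" and goes on to list electrodes and channels, followed by hook-up time and time in bed. Section 2.d adds "Participants will be videotaped during the sleep study as per our usual sleep clinic protocol". Under the close-out visit in section 2.a, a participant who wants to try another size after discussing the results has a further option: "the subject may have a repeat treatment PSG".

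Neither document names a scorer or a set of event definitions. Neither mentions coding, masking or independent reading of the recordings.

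**The concern.** AHI is obtained by scoring respiratory events on a recording, so it depends on a reader's judgement. The plan makes the device night easy to identify. It is always the later recording, so date or sequence gives it away. The stent is clipped at the nasal septum, so the video may show it. A team that followed these documents to the letter would have no instruction to hide any of this from the scorer.

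A scorer who expects the device to work may score fewer borderline events on the device night. If that shift runs in one direction across participants, it does not average out, and the planned two-night comparison cannot separate it from a device effect. The direct threat is to the single result on which the efficacy conclusion rests.

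**Working it through.** **Step 1: what the text supports.**

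| Question | Protocol and SAP |
|---|---|
| Does the primary endpoint depend on scoring? | Yes: AHI by PSG comparison (SAP) |
| Is the order fixed and device status open? | Yes: baseline without, day 8 with (protocol 2.a, 8.m) |
| Could the recording reveal the device night? | Yes: date, sequence, video (2.a, 2.d) |
| Is masked, coded or independent scoring planned? | Not mentioned |
| Is scoring stated to be unmasked? | No |

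The plan has no figure to reproduce. It gives a target of 30 participants (section 8.a) but no test, alpha, SD or expected AHI change. Everything below except n = 30 is assumed and serves as illustration only.

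**Step 2: proportional shift in scoring, by simulation.** Assumed: median AHI 18, between-person log-SD 0.8, per-night log-SD s from 0.3 to 0.5, no true device effect. For participant i, with independent standard normal z and e:

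- baseline AHI = 18 × exp(0.8 zᵢ + s eᵢ₁)
- device-night AHI = k × 18 × exp(0.8 zᵢ + s eᵢ₂), where k is the fraction of events still scored

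The test is a paired t-test on raw AHI. A false improvement is a significant fall at the nominal 2.5% in that direction. There were 20,000 simulated trials per setting.

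| Events scored on device night | s = 0.5 | s = 0.3 |
|---|---|---|
| All (k = 1.00) | about 2% | about 2% |
| 5% fewer (k = 0.95) | about 4% | 6–7% |
| 10% fewer (k = 0.90) | 7–8% | 16–17% |
| 20% fewer (k = 0.80) | about 23% | about 56% |

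On the AHI scale, mean baseline AHI in this model is 18 × exp((0.8² + s²)/2). That is 18 × exp(0.365) = 25.9 at s = 0.3 and 18 × exp(0.445) = 28.1 at s = 0.5. Shifts of 5%, 10% and 20% are therefore about 1.3–1.4, 2.6–2.8 and 5.2–5.6 events/h.

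**Step 3: absolute shift, by formula.** Assumed: paired t-test, two-sided alpha 0.05, SD of the paired difference 8 to 15 events/h, no true effect. The rejection rate comes from the noncentral t distribution with 29 degrees of freedom and noncentrality (bias / SD) × √30.

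| Bias (events/h) | SD 15: noncentrality, rejection | SD 8: noncentrality, rejection |
|---|---|---|
| 0 | 0, 5.0% | 0, 5.0% |
| 1 | 1/15 × 5.477 = 0.365, 6.4% | 1/8 × 5.477 = 0.685, 10.2% |
| 2 | 0.730, 10.9% | 1.369, 26.3% |
| 3 | 1.095, 18.5% | 2.054, 51.0% |

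With a true reduction of 3 events/h and SD 10, an added bias of 2 events/h raises the rejection rate from 35.5% to 75.4%. The same mechanism can therefore enlarge a real effect as well as create a false one.

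**The case against.** The strongest objection is that the documents do not say the recordings are scored unmasked. A reader might infer this from the word routine in section 2.a. That sentence is about electrodes and channels, though, and the reference to usual clinic practice in section 2.d concerns videotaping. A masked or separate reader would be compatible with every sentence in both documents. This stands, and it limits the point to an omission that leaves a bias possible.

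The size is also assumed throughout. Nothing in the documents supports a shift of 5%, 10% or 20%, or a shift in the same direction for every participant. The smallest shift modelled moves the error only to about 4–7%, and the largest figures need one event in five to go unscored on device nights, which is not a small bias. This stands too: the tables show sensitivity and do not estimate what will happen.

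A reader might also blame the lack of a control arm or randomised night order. Neither would by itself stop an unmasked scorer from knowing device status. Those features matter for regression to the mean and night-order effects, which are separate problems.

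Finally, masking may be imperfect. A tube in the nostril may alter the nasal-pressure signal measured by cannula. That argues for stating the limit. It is no reason to leave masking out.

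**Conclusion.** The point holds as a gap in the plan. The primary AHI comparison is open-label and in fixed order, the device night is identifiable, and no masked scoring is planned, so scorer expectation could create or enlarge the difference. The documents do not support the claim that scoring is in fact unmasked or that a resulting AHI difference would be false.

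The size cannot be determined from the documents. On the assumptions of step 2, the false-improvement rate is about 4–7%, 7–17% and 23–56% for 5%, 10% and 20% fewer events scored on the device night, against a nominal 2.5%. The results depend most on the assumed bias, then on night-to-night variability. The plan should be changed because the remedy is cheap and the primary endpoint is affected. The gap is not fatal in itself.

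**What to change.** State in the protocol and SAP that the primary AHI comes from masked scoring:

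- Give every PSG recording, including any repeat treatment PSG, a random code.
- Hide dates, video, technologist notes and device annotations from the scorer.
- Have the existing scorer read all recordings in one random order across participants, not as side-by-side pairs.
- Use one set of event definitions, fixed before scoring starts.
- State which treatment PSG supplies the primary AHI when one has been repeated, since coding alone does not settle this.

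The cost is a few sentences and the coding of about 60 recordings (30 × 2) plus any repeats. No extra participants, visits or second reader are needed. The downside is that research scoring is delayed, or baselines already read clinically are scored once more.

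The report should acknowledge what remains. Masking may be incomplete if the device alters the nasal-pressure signal or the scorer recalls a recording. Masking also does nothing about regression to the mean or night-to-night effects, so the conclusion on efficacy should be qualified for these.

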The consenting time will take about 15 minutes.

This research study is expected to last approximately one year. The active participation is up to a year. The time for the sleep questions will be about 30 minutes - the sleepiness scale will take about 5 minutes and the electronic questionnaire will take approx. 20 Min. The limit use of this device is a maximum of 10 hours - every night throughout the whole night for 7 days. At baseline and day 8 the patient will be requested to have sleep studies (without the NAS at baseline and while wearing the NAS at day 8).

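### Does the optional repeat sleep study with another stent size leave the primary AHI comparison undefined?

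*Protocol*

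**What the plan says.** Protocol section 2.a sets out the schedule: "The participants will undergo two sleep studies", the first before any use of the device and the second, wearing it, after seven days of use at home. Section 8.m dates them: "At baseline and day 8 the patient will be requested to have sleep studies".

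The close-out paragraph of section 2.a comes after both studies. It describes a "follow-up visit to discuss the results of his/her sleep studies with the study doctor". At that visit the stent is inserted and the back of the mouth is photographed, "where the nasal stent should be resting". A participant who then "would like to try the nasal stent in a different size, the subject may have a repeat treatment PSG".

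On the analysis, the SAP says: "The primary endpoint that will be evaluated in the study would be the AHI efficacy of the NAS device by PSG comparisons". The PSG measures "will be compared between the two PSG evaluations conducted", namely the initial control night without the device and "the PSG evaluation with the NAS device applied". The SAP does not mention a repeat study.

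**The concern.** A participant who repeats has three PSGs, two of them with the device. The SAP ties the control night to the initial evaluation, but it identifies the device night only by the device being worn. Both device nights fit that description, and the protocol calls the repeat a treatment study too. No rule says whether the first, the last, the better or the average night counts.

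The setting makes this worth asking. There is one arm, the primary result is a before/after change in AHI, and the option arises once results are known. AHI varies from night to night, so participants selected for a poor night tend to look better on the next one without any treatment effect. Replacing poor nights would turn that regression to the mean into apparent efficacy. Taking the better of two nights would do so whatever the reason for repeating. Either use would also mix stent sizes in one estimate.

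**Working it through.** **Step 1: which nights does the plan compare?**

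- Protocol 2.a: two studies, labelled Baseline and Treatment, with the device worn at the second.
- Protocol 8.m: the same two, at baseline and day 8.
- Protocol 2.a, close-out: the visit follows completion of the first (baseline) and second (treatment) study. The optional night comes after that and is called a repeat.
- SAP: a comparison of two PSGs, one control and one with the device.

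The SAP's two evaluations match the protocol's two numbered studies one for one. The optional night belongs to neither list. The protocol also does not say whether seven days of home use come before it, so nothing puts it on the same footing as day 8. The primary pair is baseline versus day 8.

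**Step 2: what does the repeat option do to that comparison?**

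There is no stated figure to reproduce: the documents give 30 participants but no test, level, SD or effect size. Assume no device effect and let log AHI on the baseline, day-8 and repeat nights carry independent normal errors e0, e1, e2 with SD s. The day-8 contrast is e1 - e0, with mean 0, and e2 does not enter it. Bias is therefore zero whatever share repeats. A simulation with n = 30, s = 0.35 and a one-sided 2.5% paired t-test gave 0.0% bias and a false-benefit rate of 2.4% to 2.5%.

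**Step 3: what would other uses of the repeat do?**

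Assumptions: s = 0.35; either q = 25% of participants with no improvement repeat (0.25 x 15 = 3.75 of 30, since half show no improvement by chance), or a random p = 12.5% of everyone repeats (also 3.75 of 30). With 1/√π = 0.5642, the shifts in mean log AHI are:

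- Repeat replaces day 8, non-improvers repeat: -q·s/(2√π) = -0.25 x 0.35 x 0.2821 = -0.0247.
- Repeat replaces day 8, random repeaters: 0.
- Better night used, random repeaters: -p·s/√π = -0.125 x 0.35 x 0.5642 = -0.0247.
- Better night used, non-improvers repeat: a gain arises only when e1 is the largest of the three nights (probability 1/3). The mean gap to the repeat night is then 1.5 x 1.5 x 0.5642·s = 1.2694·s. The shift is -0.25 x 0.35 x 1.2694/3 = -0.0370.

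Exponentiating gives the AHI change. The false-benefit rates come from simulation (100,000 trials per case).

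| Night used | Who repeats | AHI change | False-benefit rate |
|---|---|---|---|
| Day 8 | anyone | 0.0% | 2.4% to 2.5% |
| Repeat replaces day 8 | random | 0.0% | about 2.5% |
| Repeat replaces day 8 | non-improvers | -2.4% | 4.7% |
| Better of two | random | -2.4% | 4.5% |
| Better of two | non-improvers | -3.6% | 6.1% |

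**Step 4: how firm are these sizes?**

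They are not firm. If every non-improver repeated (15 of 30), the figures would be -9.4% and 21% for replacement, and -13.8% and 48% for the better night. If the repeaters were the 4 of 30 with the worst results, they would be -4.9% and 10.5%, and -5.5% and 12.6%. Varying s from 0.25 to 0.50 moves the -2.4% replacement figure between -1.8% and -3.4%. The direction is secure, but the size depends on choices that the documents do not inform.

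**The case for a change.** The best argument for acting is that a schedule of visits does not define an analysis. Sections 2.a and 8.m say when PSGs happen, and only the SAP says what is compared. The SAP pins down the control night with one word and leaves the device night without one. With no control arm, nothing in the data would reveal the selection effect, and confirming the rule would cost one sentence.

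Part of this stands. No explicit rule exists, and the possible bias runs in the device's favour. But harm needs steps that the documents do not contain. Replacement biases the result only if repeating is linked to a poor AHI and the analyst also discards the scheduled night. The stated trigger is the wish for another size, at a visit where the stent's position is inspected, so fit is at least as likely a reason. The better-night route needs an analyst to adopt a best-of-two rule that nothing in either document suggests.

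A blanket ban on the repeat ever standing in for day 8 would also go further than the gap requires. It would not say what to do when the day-8 recording is missing or unusable, and it would rule out a prespecified result for the fitted size, which is also a legitimate question.

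**Conclusion.** No change to the plan is needed. The numbered and dated studies in the protocol and the two-PSG comparison in the SAP point to baseline versus day 8. On that reading the optional repeat adds no bias and leaves the error rate at its nominal level, however many participants repeat. A sentence saying so would record what the plan already implies. It would do no harm, as would listing any repeat nights descriptively by stent size, but the analysis would be the same.

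This conclusion rests on the text and needs none of the assumed figures. The sizes for other uses of the repeat (0% to -3.6% in AHI with about 3.8 of 30 repeating, and larger if more repeat or the worst results are singled out) depend on an assumed SD, test, repeat share and selection pattern. They show which way a departure from the plan would lean and do not estimate anything in this trial. A report that used the repeat or the better night as the primary value would be such a departure and should be read with that in mind.

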3. BACKGROUND

a. Past Experimental and/or Clinical Findings

Nasal airway stents have been tried in sample populations with mixed results. The sponsor of the proposed study has developed several versions of their device, of which the device for the proposed study appears to be the most promising as tested in a few subjects by the sponsor in an internal study.

b. Findings from Past Animal Experiments

Not Applicable

4. RADIOISOTOPES OR RADIATION MACHINES

a. Standard of Care (SOC) Procedures

Identify Week/Month of Study	Name of Exam	Identify if SOC or Research
NA	NA	NA

b. Radioisotopes

i. Radionuclide(s) and chemical form(s)

NA

	ii.	Total number of times the radioisotope and activity will be administered (mCi) and the route of administration for a typical study participant		
		NA		
	iii.	If not FDA approved: dosimetry information and source documents (package insert, Medical Internal Radiation Dose [MIRD] calculation, and peer reviewed literature)		
		NA		
c.	R	adiation Machines – Diagnostic Procedures		
	i.	Examination description (well-established procedures)		
		NA		
	ii.	Total number of times each procedure will be performed (typical study participant)		
		NA		
	iii.	Setup and techniques to support dose modeling		
		NA		
	iv.	FDA status of the machine and information on dose modeling (if procedure is not well-established)		
		NA		
d.	R	Radiation Machines – Therapeutic Procedures		
	i.	Area treated, dose per fraction/number of fractions, performed as part of normal clinical management or due to research participation (well-established procedures)		
		NA		
	ii.	FDA status of the machine, basis for dosimetry, area treated, dose per fraction and number of fractions (if procedure is not well-established)		

NA

